## Annex 9. Village Reporter CRF

### A. DETAILS OF THE DECEASED

0.	District / Sub-District /Community	
1.	Serial number	
2.	Full name of deceased	
3.	Date of birth (day/month/year)	
4.	Sex of deceased	
5.	Date of death (day/month/year)	
6.	Place of death	
7.	Usual place of residence	
8.	RTS,S status (if feasible)	

### B. DETAILS OF THE INFORMANT

1.	Full name of informant	
2.	Address	
3.	Telephone number	
4.	Date of reporting	

Note: This is not a burial permit or a death certificate.

#### DECLARATION

I ..... do hereby declare

that I have been notified of the death of

..... and permission is hereby

granted for the burial of the deceased after the registration of the death with the Birth

and Death Registry.

Name: .....

Title: .....

Signature .....  
Date (D AY/MONTH/YEAR) .....

## Annex 10. CRF for impact evaluation

Variable format/type	Question
Select one GHA/KEN/MLW	Country
Select one YES or NO	Was consent obtained ?
Alphanumeric	If Y, then include unique identifier of consent form
Death reported	
day/month/year	Date death reported
Alphanumeric	ID of the VR
Demographics	
Drop down	Cluster
Drop down list	Village name
Text	Name of respondent
Drop down list	Relation of respondent
Date	Date of VA interview
XX:XX hrs	Time of VA interview
Text	Compound head name (KENYA ONLY)
Text	What was the first or given name(s) of the deceased?
Text	What was the surname (or family name) of the deceased?
Text	Initials of the deceased
Select one MALE or FEMALE	What was the sex of the deceased?
Select one YES or NO	Is the date of birth known?
Date	When was the deceased born?
Select one YES or NO	Is the date of death known?
Date	When did (s)he die?
Number	How old was the deceased when they died (Age at death in months)
Select LOCATION from drop down list	What was her/his place of death?
Select HOME or HEALTH FACILITY or OTHER	Where was her/his place of death?
Select IMPLEMENTING or COMPARATOR cluster	What was her/his place of usual residence? (the place where the person lived most of the year)
Drop down list	Cluster of residence
Period (months)	How long had the deceased lived there?
Longitude	Longitude GPS coordinates of the household

Latitude	Latitude GPS coordinates of the household
Select one YES or NO	Did the deceased receive any vaccinations since birth?
Select one YES or NO	Is there a vaccination record available
Photo taken YES or NO	If YES to vaccination record available, take a photograph of the vaccine record
Select one HEALTH RECORD OR MATERNAL RECALL or HEALTH FACILITY REGISTER	Record vaccines received
Date	BCG
Date	OPV 0
Date	OPV 1
Date	OPV 2
Date	OPV 3
Date	IPV
Date	Pentavalent 1
Date	Pentavalent 2
Date	Pentavalent 3
Date	PCV 1
Date	PCV 2
Date	PCV 3
Date	RTS,S 1
Date	RTS,S 2
Date	RTS,S 3
Date	RTS,S 4
Date	Rotavirus vaccine 1
Date	Rotavirus vaccine 2
Date	Measles 1
Date	Measles 2
Date	Meningitis A vaccine
Date	Yellow fever vaccine
Select one YES or NO	Was VA form completed
Number	Provide the VA form ID
Alphanumeric	Unique ID of person conducting VA

Alphanumeric	Unique ID of person reviewing VA
--------------	----------------------------------

Question on the variable list	Instructions and notes
Time of VA start	For QA purposes
Time of VA end	For QA purposes

# Annex 11. Vaccination Registry

#	Name	Address	Date of Birth	BCG	OPV I	OPV II	OPV III	IPV I	IPV II	IPV III	Pentta I	Pentta II	Pentta III	PCV I	PCV II	PCV III	MR I	MR II	YF I	
1																				
2																				
3																				
4																				
5																				
6																				
7																				
8																				
9																				
10																				
11																				
12																				
13																				
14																				
15																				
16																				
17																				
18																				
19																				
20																				
21																				
22																				
23																				
24																				
25																				
26																				
27																				
28																				
29																				
30																				
31																				
32																				
33																				

## Annex 12. Sentinel hospital CRF

Type	Question	
Select one GHA/KEN/MLW	Country	
Select one YES or NO	Has consent been obtained ?	
Alphanumeric	If Y, then include unique identifier of consent form	
Drop down list	Name of sentinel hospital	
Number	Indicate the inpatient number for this admission	
Text	What is the first or given name(s) of the child ?	
Text	What is the surname (or family name) of the child?	
Text	Initials of the child (use 3 letters)	
Demographics		
Select IMPLEMENTING or COMPARATOR cluster	What is her/his place of usual residence? (the place where the person lived most of the year)	
Text or drop down	Cluster of residence	
Select one YES or NO	Have the child been resident in this location during this illness?	
Select one MALE or FEMALE	What is the sex of the child?	
Select one YES or NO	Is the date of birth known?	
YYYY	When is the child born?	
MMM	When is the child born?	
DD	When is the child born?	
DDMMMYYYY	What is the date of this admission ?	
Number	Age at admission (months)	
Select one YES or NO	Is this the first admission ?	
Number	If not the first admission, indicate number of previous admissions in the last 12 months	
YYYY	If not the first admission, indicate the date of the last admission	
MMM	If not the first admission, indicate the date of the last admission	
DD	If not the first admission, indicate the date of the last admission	
Select one YES or NO	Is the child enrolled in a clinical or intervention trial ?	

Select one YES or NO	Does the child have a bed net ?	
Select one YES or NO	Does the child sleep under a bed net on the night before admission?	
Select one YES or NO	At any time in the last 12 months has anyone sprayed the interior walls of your dwelling against mosquitoes ?	
Vaccinations	For all children, just record RTS,S status; then if there is a meningitis or cerebral malaria, record all vaccines.	
Select one YES or NO	Did the child receive any vaccinations since birth?	
Select one YES or NO	Is there a vaccination record available	
Confirm if photo taken YES or NO	If vaccination record is available, take a photograph	
Select one HEALTH RECORD OR MATERNAL RECALL	Record vaccines received	
Date	BCG	
Date	OPV 0	
Date	OPV 1	
Date	OPV 2	
Date	OPV 3	
Date	IPV	
Date	Pentavalent 1	
Date	Pentavalent 2	
Date	Pentavalent 3	
Date	PCV 1	
Date	PCV 2	
Date	PCV 3	
Date	RTS,S 1	
Date	RTS,S 2	
Date	RTS,S 3	
Date	RTS,S 4	
Date	Rotavirus vaccine 1	
Date	Rotavirus vaccine 2	
Date	Measles 1 or Measles Rubella 1	
Date	Measles 1 or Measles Rubella 2	
Date	Meningitis A vaccine	
Date	Yellow fever vaccine	

This admission		
History		
Select one YES or NO	Has the child had fever in the last 7 days ?	
Date	Indicate the date the fever started	
Number	How many days has the child had fever	
Select one YES or NO	Have you sought treatment for the fever in the last 7 days ?	
Select one YES or NO	If sought treatment, was an antibiotic given?	
Drop down list	If Yes to antibiotic, which antibiotic was used ?	
Select one YES or NO	If sought treatment, was an antimalarial given?	
Drop down list	If Yes to antimalarial, which antimalarial was used ?	
Select one YES or NO	Does this child have any pre-existing illnesses?	
Select one HIV, Congenital heart disease, Sickle cell disease, Severe malnutrition, other	Indicate the pre-existing illnesses	
Select one YES or NO	Has the child had difficulty in breathing during this illness?	
Select one YES or NO	Has the child had altered consciousness during this illness?	
Select one YES or NO	Has the child had convulsions during this illness?	
Select one YES or NO	If yes to convulsions, number in the last 24 hours?	
Number	Has the child had more than 1 convulsion or atypical convulsion during this illness?	if yes, do LP.
Examination		
Number ( _ _ . _ C)	What was the body temperature on admission?	
Number ( _ _ Breaths per min )	What was the respiratory rate on admission?	
Number ( _ _ . _ kg)	What was the weight taken on admission?	
Number ( _ _ . _ cm)	What was the MUAC taken on admission?	
Number (1-5)	What was the total Blantyre coma score on admission?	if total score is 3 or less, do LP
Number (0, 1 or 2)	Motor component	
Number (0, 1 or 2)	Verbal component	

Number (0 or 1)	Eye component	
Select one YES or NO	Was there presence of deep breathing on admission?	
Select one YES or NO	Was there presence of lower chest indrawing on admission?	
Select one YES or NO	Was there a bulging fontanelle on admission? For children less than 12 months of age	if yes, do LP
Select one YES or NO	Was there neck stiffness on admission?	if yes, do LP
Select one YES or NO	Was the child eligible for a lumbar puncture ? Contraindications for LP include needing resuscitation, Poor pupillary responses to light, papilloedema, cranial nerve lesions, lateralising signs, Skin infection at LP site	Review for contraindications to LP, then if not present, do LP
Text	If eligible for LP but not done, describe reasons.	
Tests		
Select one YES or NO or not done	Was an RDT or malaria slide performed ?	
Select one YES or NO or not done	Results of the RDT or malaria slide	
Select one YES or NO or not done	Was an Haemoglobin or haematocrit test performed ?	
Number ( _ . _ . _ or _ _ %)	Results of the haemoglobin or haematocrit test	
Select one YES or NO or not done	Was an Blood glucose test performed ?	If BCS is less than 3
Number ( _ . _ . _ mmol/L)	Results of the blood glucose test	
Select one YES or NO or not done	Was a lumbar puncture performed ?	Review criteria for LP
Date	Date of lumbar puncture	
Alphanumeric	ID of person performing LP	
Select one YES or NO	Had antibiotics been used in the 7 days before LP?	If yes, refer to question above for antibiotics used
Select reason: Contraindication for LP, parental refusal, dead, absconded, discharge against medical advice, referral to another facility, no resources	If no LP was performed with criteria present	
Select one YES or NO or not done	Was CSF collected ?	

Alphanumeric	CSF sample number	
Select CLEAR, TURBID, PURULENR, BLOODY, OTHER	Macroscopic appearance of the CSF	
Select one YES or NO or not done	Was CSF WCC counted ?	
Number ( _ _ _ )	Results of CSF WCC count	
Select one YES or NO or not done	Was a CSF aliquot frozen?	
To be inputted from the ref lab	CSF result from reference laboratory	
Diagnosis		
ICD 10 classification code	Final primary diagnosis	
If final primary diagnosis is not consistent with clinical algorithm, record reason for discrepancy (e.g. severe malaria anemia or cerebral malaria with negative blood slide because treated confirmed malaria prior day, or low BCS with parasites, but not CM)		
ICD 10 classification code	Secondary diagnosis 1	
If final secondary diagnosis 1 is not consistent with clinical algorithm, record reason for discrepancy		
ICD 10 classification code	Secondary diagnosis 2	
If final secondary diagnosis 2 is not consistent with clinical algorithm, record reason for discrepancy		
ICD 10 classification code	Secondary diagnosis 3	
If final secondary diagnosis 3 is not consistent with clinical algorithm, record reason for discrepancy		
Select ALIVE; DEAD, REFERRED or ABSCONDED	Outcome	
QA		
Alphanumeric	ID of person completing admission form	
Alphanumeric	ID of person reviewing/finalising inpatient form	

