- History of fever, difficulty breathing, convulsions, altered consciousness.
- Findings from physical examination including body temperature, respiratory rate, presence of chest indrawing, deep breathing, the components of the Blantyre Coma Score, neck stiffness, bulging fontanelle.
- Whether a blood sample was collected and, if so, the tests requested, results available during the admission and sample identification number for tests requested off the paediatric ward. All children will be expected to have a malaria test (RDT and microscopy) and a haemoglobin/PCV.

In addition, children under 2 years of age with a BCS <3, or assessed as P or U on AVPU score, or aged 2 years and over and with a Glasgow Coma Score <11, will have the following data captured:

- Blood glucose result
- Whether a CSF sample was collected and, if so, the sample identification number and results available during admission.

At the time of discharge a final main and any secondary diagnoses will be recorded by the attending clinician, taking into account the clinical assessments, available test results, evolution of the illness and response to treatment, and the final outcome (alive, dead, referred, absconded).

All data will be recorded in a record form (CRF) and entered into the programme’s database.

---

 AVPU: Alert, responding to Voice, responding to Pain, Unresponsive

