### **Severe malaria**

- Plasmodium parasitaemia (> 0 detected/  $\mu$ L) detected by RDT (or microscopy in the absence of an RDT result)

AND

- One or more of the following;
  - Impaired consciousness: a Glasgow coma score < 11 in children  $\geq 2$  years of age, a Blantyre coma score < 3 in children < 2 years of age, or child responding only to pain or unresponsive;
  - Multiple or atypical convulsions: more than two episodes within 24 h;
  - or prolonged at >15 minutes, or focal;
  - Respiratory distress (manifesting as chest indrawing or deep breathing);
  - Severe malarial anaemia: haemoglobin concentration  $\leq 5$  g/dL or a haematocrit of  $\leq 15\%$  ;

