## 10.7 Variables

At sentinel hospitals the Case ID, Hospital ID, Date of admission, age at admission, gender, residence location, vaccination dates and doses, signs and symptoms at recruitment, samples of interest collected during admission and the code to identify the sample, and the final diagnosis (ICD 10 – or later - code) will be captured. Results from the external laboratory and the review of

the expert panel will allow the final classification of each hospital admission with the following key variables:

- Admission Date
- Age at admission
- Date of birth
- Date of death (when applicable)
- Gender
- Residence location (to permit calculation of distances e.g. to hospital)
- Cluster ID
- RTS,S/AS01 vaccination status (number and dates of doses received); health card or recall (no dates for recall)
- Other vaccination status (type of vaccine, number and dates of doses received); health card or recall (no dates for recall)
- Results of malaria microscopy and RDT at admission
- Severe Malaria
- Cerebral Malaria
- Anaemia
- Meningitis suspected
- Meningitis probable
- Meningitis etiologically confirmed at hospital level
- Meningitis etiological confirmed at reference laboratory level
- Etiology agent confirmed at hospital level
- Etiology agent confirmed at reference laboratory level
- (Other outcomes).

A Geographic Information System will be used to map the residence locations of inpatients in the sentinel hospitals and the population at risk in the catchment area will be obtained disaggregating the population count data to a finer spatial detail (see below).

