Mortality (all causes)	Death due to any cause
Malaria-associated mortality in hospital	Death in hospital in an individual who has confirmed malaria
Severe malaria	P.falciparum infection detected by RDT (antigenaemia detected by RDT or in the absence of RDT result, parasitaemia by microscopy at any density) AND one or more of the following: a) impaired consciousness (Glasgow coma score <11, Blantyre coma score <3, or assessed as P or U on the AVPU score and not positive for probable or confirmed meningitis; b) multiple of atypical convulsions (more than two episodes within 24 hours or prolonged (>15minutes), or focal) and not positive for probable or confirmed meningitis; c) respiratory distress (manifested as chest indrawing or deep breathing); d) severe malaria anaemia (haemoglobin concentration <5g/dL or haematocrit <15%).
Cerebral malaria (broader)	P.falciparum infection (by RDT or microscopy, as above) with impaired consciousness (Glasgow coma score <11 or Blantyre coma score <3 or assessed as P or U on AVPU score), excluding cases with CSF findings consistent with probable meningitis.
Cerebral malaria (stricter, LP required)	P.falciparum infection (by RDT or microscopy, as above) with impaired consciousness (Glasgow coma score <11 or Blantyre coma score <3 or assessed as P or U on AVPU score) AND CSF findings not consistent with probable meningitis (this strict cerebral malaria diagnosis cannot be made without an LP).
Severe malaria (stricter)	P.falciparum infection (as above) AND one or more of the following: a) impaired consciousness (Glasgow coma score <11, Blantyre coma score <3, or assessed as P or U on the AVPU score and negative for meningitis (LP performed); b) multiple of atypical convulsions (more than two episodes within 24 hours or prolonged (>15minutes), or focal) and negative for meningitis (LP performed); c) respiratory distress (manifested as chest indrawing or deep breathing); d) severe malaria anaemia (haemoglobin concentration <5g/dL or haematocrit <15%).
Probable meningitis	Children will be considered to have “probable meningitis” if in a suspected case*, the macroscopic aspect of the CSF is turbid, cloudy or purulent; or the CSF leukocyte count is >10 cells/mm ³ .
Confirmed meningitis	Any suspected or probable case, laboratory confirmed by culture or PCR to be of bacterial, viral or other aetiology in the CSF.

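### The sentinel-hospital CRF (Annex 12) has no field for Glasgow or AVPU scores, prolonged or focal seizures or, as typed, a 24-hour seizure count, and it merges RDT with microscopy, so some arms of the severe malaria, cerebral malaria and suspected meningitis definitions cannot be derived

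*Protocol*

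**What the plan says.** Protocol 10.3.3 directs that data on every admitted child aged 1 to 59 months go into a CRF and cites Annex 12 as that form. Protocol 10.9 says an algorithm will classify admissions by the definitions in 10.4. SAP section 5 says outcomes are defined in its Table 3 and in the protocol, so both sets govern.

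- **Coma.** Protocol 10.3.3 splits the scales by age: Blantyre below 3 or P/U on AVPU under 2 years, and for older children "aged 2 years and over and with a Glasgow Coma Score <11". Protocol 10.4.2 also uses Glasgow from 2 years and Blantyre below that age, with P/U as an alternative. SAP Table 3 accepts any of the three scales at any age. Annex 12 asks "What was the total Blantyre coma score on admission", typed as a number from 1 to 5, followed by components such as "Number (0, 1 or 2) Motor component".
- **Seizures.** The protocol's severe malaria definition has "Multiple or atypical convulsions: more than two episodes within 24 h", or prolonged over 15 minutes, or focal. SAP Table 3 matches it: "more than two episodes within 24 hours or prolonged (>15minutes), or focal". Suspected meningitis needs two or more in 24 hours. Annex 12 has "If yes to convulsions, number in the last 24 hours" with response type yes/no. The next row asks whether there was more than one convulsion, or an atypical one, during the illness, and is typed as a number.
- **Malaria test.** Protocol 10.7 lists "Results of malaria microscopy and RDT at admission". The severe malaria definitions use microscopy only when there is no RDT result. Annex 12 has a single item, "Results of the RDT or malaria slide".

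**The concern.** The classification algorithm can use only what the form holds. If a child of 2 years or over is scored on Glasgow, as 10.3.3 and 10.4.2 expect, or a child of any age is assessed on AVPU, Annex 12 offers no place for the result. If a child with parasitaemia has one long or focal seizure, no item captures the feature that makes the case severe malaria. If RDT and slide disagree, the record does not show which result was entered.

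At stake are arms of a primary safety endpoint (cerebral malaria) and a primary impact endpoint (severe malaria), and one entry route to suspected meningitis. Lost cases also cost power: SAP Table 5 counts on 400 cerebral malaria and 4000 severe malaria events for 90% power. The within-cluster comparison group (group B) includes older children, so both sides of the eligible to non-eligible ratio are exposed.

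**Working it through.** There is no planned figure to reproduce. The check sets each element of the definitions against Annex 12, then tests what each gap changes.

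**1. Definition elements against the form**

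| Element | Needed by | Annex 12 | Derivable? |
|---|---|---|---|
| Blantyre below 3 | 10.4.1, 10.4.2, SAP Table 3 | Total and three components | Yes |
| Glasgow below 11 | 10.3.3, 10.4.1, 10.4.2, SAP Table 3 | None | No |
| P or U on AVPU | same | None | No |
| Seizures in 24 h: 2 or more, more than 2 | 10.4.1, 10.4.2, SAP Table 3 | Typed yes/no | Not as typed |
| Seizure over 15 min, or focal | 10.4.2, SAP Table 3 | None of its own | No |
| Respiratory distress, haemoglobin or haematocrit | 10.4.2, SAP Table 3 | Present | Yes |
| Neck stiffness, fontanelle, CSF appearance and cell count | 10.4.1, SAP Table 3 | Present | Yes |
| RDT and microscopy separately | 10.7, 10.4.2, SAP Table 3 | One shared result | No |

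**2. Blantyre range.** Motor 0–2, verbal 0–2 and eye 0–1 give 3 × 3 × 2 = 18 combinations, with totals from 0 to 5. One combination gives 0, which a field running from 1 to 5 cannot hold. Entering that 0 as 1 changes the below-3 classification in 0 of 18 combinations, and the true total can be rebuilt from the components. The range is wrong but has no effect on classification.

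**3. Seizure count.** With 1, 2 or 3 seizures in 24 hours, a yes/no item reads yes each time. The meningitis criterion (2 or more) is no, yes, yes, and the severe malaria criterion (more than 2) is no, no, yes. The item separates neither 1 from 2 nor 2 from 3. The next row does not repair this, because it covers the whole illness and mixes repeated with atypical seizures. Its instruction column begins with if yes, which suggests that the two response types were swapped. Swapping them back restores the count but still leaves no item for duration or focality.

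**4. Exposure at age 2 years or over.** This assumes steady births, no deaths, and group A1 followed to month 46. With entry at time s, eligible person-time is the integral of (46 − s) from 0 to 46, which is 46²/2 = 1058.

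- Malawi (entry at 5 months, 24 months of age reached 19 months later): (46 − 19)²/2 = 27²/2 = 364.5, and 364.5/1058 = 34.5%.
- Ghana (entry at 6 months): (46 − 18)²/2 = 28²/2 = 392, and 392/1058 = 37.1%.
- Kenya: without catch-up, the same 37.1%. SAP section 7 admits children born from 1 September 2018, so those aged 6 to 12 months at the start are added. They contribute 6 × 46 = 276 to the total. A child aged a months at the start spends 46 − (24 − a) = 22 + a months at age 2 or over, and the integral from 6 to 12 is 132 + 54 = 186. The share is (392 + 186)/(1058 + 276) = 578/1334 = 43.3%.
- At month 24 after a country's own start, the share is 5²/2 ÷ 24²/2 = 12.5/288 = 4.3% in Malawi and 6²/2 ÷ 288 = 18/288 = 6.3% in Ghana.

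**5. Form prompts.** The lumbar puncture prompt for coma fires at a Blantyre total of 3 or less, while the definitions use below 3. The two rules differ in 5 of the 18 component combinations (those that total 3). The coma prompts for lumbar puncture and blood glucose use Blantyre only, so a child who qualifies on Glasgow or AVPU triggers neither.

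**The case against.** The strongest reply is that most cases remain classifiable, and much of this stands.

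- A reader might infer that a 3-year-old in coma cannot meet the definition at all. The documents do not support that. Protocol 10.3.3 asks for the Blantyre components without an age limit, Annex 12 sets none, and SAP Table 3 accepts Blantyre below 3 at any age.
- A reader might infer that the 1-to-5 range hides the deepest coma. It does not (step 2).
- A reader might infer that severe malaria as a whole cannot be computed. It is an any-of definition whose Blantyre, respiratory distress and anaemia arms are all captured, and protocol 8.2.1 summarises it as severe malaria anaemia or cerebral malaria. Suspected meningitis likewise has other routes, including clinical judgement, and the primary meningitis outcome turns on CSF findings that the form holds.
- The yes/no count looks like a transposition, and an error in reading the table from PDF cannot be fully excluded.
- Annex 12 may not be the fielded form. Annex 1 dates it July 2018, before protocol version 9, its notes read as drafting remarks, and SAP section 21 describes tested country databases with range checks. Those eCRFs are not in the documents.
- A shared malaria result matters for classification only when both tests are done and disagree.

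These points limit the size of the problem but do not remove it. Version 9 still carries Annex 12 as the form, and nothing in the documents shows that the missing items are collected elsewhere.

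**Conclusion.** The point holds for specific arms. As written, Annex 12 cannot record the Glasgow or AVPU branches of impaired consciousness, prolonged or focal seizures, or the 24-hour seizure count, and it does not keep RDT and microscopy apart. What is lost is cases that qualify only through one of those arms, together with the ability to apply the protocol's age-specific coma rule.

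The size of that loss cannot be derived from the documents. It is tempting to read the 34% to 37% of eligible person-time at age 2 years or over (about 43% in Kenya with catch-up) as the share of cases lost. It is only the time during which the protocol's Glasgow rule applies, and it would become loss only for children never scored on Blantyre. Nor is a direction of bias shown, since the same form serves both arms.

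The conclusion assumes that the fielded eCRF follows Annex 12 and that the field types were read correctly from the PDF. If the eCRF already has the fields, only the annex is out of date.

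**What to change.** In Annex 12 and the eCRF:

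1. Add a Glasgow total for children aged 2 years and over, and an AVPU field.
2. Make the 24-hour seizure count numeric and the following item yes/no, and add yes/no items for a seizure over 15 minutes and for a focal seizure.
3. Record RDT and microscopy results in separate fields. A parasite count is optional and not part of the error.
4. Correct the Blantyre total to 0–5, ideally summed from its components. This is a tidy-up with no effect on classification.

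Reconcile the age-specific coma rule in protocol 10.4.2 with SAP Table 3, which has no age split. Reconcile the CRF's lumbar puncture prompt with the threshold in the definitions, and its Blantyre-only coma prompts with the scales named in 10.3.3.

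The cost is a form revision of a few items and no new procedures. Protocol Table 5 already expects every hospital level to record Blantyre or Glasgow scores and multiple convulsions. For records already collected, first check what the live eCRFs hold. Blantyre totals can be rebuilt from the components, but Glasgow scores, seizure duration and focality cannot be recovered from a form that never asked for them.
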